1.0 Background

Since drugs for hypertension are generally used for a long period of time, the safety of long-term use must be established. While the safety of long-term use of Zacras Combination Tablets LD & HD (hereinafter referred to as Zacras Combination Tablets) was already evaluated in a Japanese Phase III long-term clinical study (duration of treatment: 52 weeks, number of evaluated subjects: 368), it is necessary to evaluate the safety in more patients in clinical settings after marketing, a population that, unlike the study population, receive the drug in diverse situations.

Accordingly, a specified drug-use survey (hereinafter referred to as the survey) is planned to evaluate the safety and efficacy of long-term use of Zacras Combination Tablets in hypertensive patients in daily medical practice. This survey will be conducted in compliance with Good Post-marketing Study Practice (GPSP) ordinance and related requirements.

2.0 Objectives

To evaluate the safety and efficacy of long-term use of Zacras Combination Tablets in hypertensive patients in daily medical practice

3.0 Planned Sample Size and Rationale

3.1 Planned Sample Size

1,000 patients

3.2 Rationale

Patient populations identified as important missing information from Japanese clinical studies of Zacras Combination Tablets are patients with renal impairment, patients with hepatic impairment, and elderly patients (≥ 75 years old). The sample size required to evaluate the safety and efficacy of long-term use of Zacras Combination Tablets in these patient populations was calculated by reference to previous results. More specifically, according to final tabulation (number of patients included in safety evaluation: 3,300) in a previous specified drug-use survey (long-term use survey in hypertension) of a fixed-dose combination (UNISIA Combination Tablets) of an angiotensin receptor blocker (ARB) (candesartan) and a Ca antagonist (amlodipine), which belongs to the pharmacologically same class as Zacras Combination Tablets, patients with renal impairment, patients with hepatic impairment, and elderly patients (and those ≥ 75 years old) accounted for 6.9%, 11.5%, and 65.2% (36.8%) of all patients, respectively. According to final tabulation (number of patients included in safety evaluation: 4,152) in a drug use-results survey of candesartan alone (BLOPRESS Tablets), patients with renal impairment, patients with hepatic impairment, and elderly patients (and those ≥ 75 years old) accounted for 9.5%, 10.6%, and 53.2% (22.1%), respectively. With a target sample size of 1,000 patients for the present survey, 70 patients with renal impairment, 100 patients with hepatic impairment, and 500 elderly patients (and 200 patients ≥ 75 years old)

are expected to be collected, probably allowing the safety and efficacy evaluation in these populations. This calculation is not based on statistical estimation.

4.0 Survey Population

The survey population consists of hypertensive patients who do not meet any of the exclusion criteria listed in Section 4.1. Refer to the “Precautions for Indication” (presented below) and “Precautions” sections in the package insert.

<Precautions for Indication>

Zacras Combination Tablets should not be used as the first-line treatment of hypertension. An excessive drop in blood pressure may occur.

4.1 Exclusion Criteria

Patients who meet any of the following criteria should be excluded from the survey:

- (1) Patients with a history of hypersensitivity to any of the ingredients of Zacras Combination Tablets or other dihydropyridines
- (2) Patients who are or may be pregnant
- (3) Diabetic patients taking aliskiren fumarate (excluding those with markedly poor blood pressure control despite other antihypertensive treatments)

5.0 Dosage and Administration

For adults, one Zacras Combination Tablet (20 mg/2.5 mg or 20 mg/5 mg of azilsartan/amlodipine) will be administered orally once daily. Zacras Combination Tablets should not be used as the first-line treatment of hypertension. Refer to the “Precautions for Dosage and Administration” (presented below) and “Precautions” sections in the package insert.

<Precautions for Dosage and Administration>

- (1) It should be determined whether Zacras Combination Tablets are indicated for each patient individually based on the following Dosage and Administration and Precautions for Dosage and Administration of azilsartan and amlodipine besilate, as well as other relevant information:

Azilsartan

Dosage and Administration

For adults, azilsartan 20 mg should usually be administered orally once daily. The dose may be increased or reduced as appropriate based on age and symptoms, with the maximum daily dose being 40 mg.

Precautions for Dosage and Administration

It should be carefully determined whether or not azilsartan is indicated while keeping the hypotensive effect of azilsartan in mind. Initiation of treatment at a low dose below 20 mg should also be considered.

Amlodipine besilate

•Hypertension

Dosage and Administration

For adults, amlodipine 2.5 to 5 mg should usually be administered orally once daily. The dose may be increased or reduced as appropriate based on symptoms. In the case of insufficient response, the dose may be increased up to 10 mg given once daily.

(2) As a general rule, switching to Zacras Combination Tablets should be considered for patients receiving azilsartan 20 mg with amlodipine 2.5 to 5 mg or patients with poor blood pressure control despite treatment with either one of these treatments.

6.0 Planned Number of Medical Institutions by Department

Internal medicine and other departments Approximately 250 medical institutions

7.0 Methods

7.1 Observation Period

12 months

7.2 Request to and Contract with the Study Site

Request and contract for participation in the survey will be made using a paper case report form (CRF). A representative of Takeda Pharmaceutical Company Limited (hereinafter referred to as Takeda's representative) will explain the objectives, contents, and methods of the survey to the investigator based on "Request for cooperation for specified drug-use survey," "Implementation outline," "Patient registration form (sample)," and "Case report form (sample)" to enter into a written contract with the study site and request the study site to conduct a survey within a specified period.

7.3 Method of Patient Registration

Patients will be registered using the central registration system via fax. After the start of the contract with the study site, the investigator shall register each patient for whom Zacras Combination Tablets are prescribed by faxing a patient registration form containing patient registration information (refer to Section 9.1) to the central registration center (refer to Section 12.2) within 14 days after prescription of Zacras Combination Tablets (day of prescription designated as day 0 and day following the day of prescription designated as 1 day after prescription). No patient can be registered before Zacras Combination Tablets are actually prescribed. Patients determined by the central registration center to be ineligible for any reason cannot be registered. The investigator shall register a new patient using a new patient registration form supplied by Takeda's representative.

Takeda's representative will supply a CRF, which will be issued after the central registration

center decides to register the relevant patient, to the investigator.

7.4 Completion and Submission of Case Report Form

For each of all registered patients, the investigator shall complete and submit a CRF to Takeda Pharmaceutical within approximately 1 month after the end of the observation period. Any failure to confirm the intake of Zacras Combination Tablets shall be specified (no further information is required).

For patients discontinued from treatment with Zacras Combination Tablets for any reason during the observation period, the investigator shall complete and submit a CRF to Takeda Pharmaceutical within approximately 1 month after the end of required observation. For any patient discontinued from treatment with Zacras Combination Tablets due to an adverse event, the investigator shall complete and submit a CRF to Takeda Pharmaceutical after monitoring the patient as long after discontinuation of treatment as possible until the adverse event is confirmed to have resolved or be resolving.

7.5 Actions to be Taken in Case of Serious Adverse Events

The investigator shall immediately communicate any serious adverse event in the observation period to Takeda's representative. In addition, the investigator shall provide detailed information at the request of Takeda's representative.

8.0 Planned Period

Survey period: From June 2014 to 31 January 2017

Patient enrollment period: From June 2014 to 31 January 2016^{Note)}

^{Note)} Patient registration (receipt of a patient registration form via fax) will not be accepted on 1 February 2016 onwards even if Zacras Combination Tablets are prescribed by 31 January 2016.

If the number of patients enrolled in the survey reaches the planned sample size before 31 January 2016, acceptance of registration will be terminated before the end of the patient enrollment period. If the patient enrollment period is shortened, the survey period will be changed accordingly.

9.0 Survey Items

The investigator shall enter the items listed below into the patient registration form and the CRF. The survey schedule is presented in Appendix.

9.1 Entries into the Patient Registration Form

1) Survey items

Name of the medical institution, name of a physician who completes the patient registration form, date of prescription of Zacras Combination Tablets, patient identification number, patient initials, sex, date of birth, assessment based on the inclusion criteria, assessment

based on the exclusion criteria, presence or absence of breast-feeding (only females)

2) Time points of survey

At patient registration

9.2 Entries into the Case Report Form

9.2.1 Cover of the Case Report Form

Date of final entry into the CRF, name of a physician who completes the CRF

9.2.2 Patient Demographics and Baseline Characteristics

1) Survey items

Time of diagnosis of hypertension, diagnostic category (at the start of treatment with Zacras Combination Tablets), predisposition to hypersensitivity (presence or absence and details), concurrent illness (presence or absence and details), medical history (presence or absence and details), height, body weight, smoking history, drinking history, presence or absence of breast-feeding (at the start of treatment with Zacras Combination Tablets) [only females]

2) Time points of survey

At the start of treatment with Zacras Combination Tablets

9.2.3 Treatment Given

1) Survey items

Details on the use of Zacras Combination Tablets (daily dose, duration of treatment, and reason for discontinuation of treatment), details on the use of other antihypertensive* (presence or absence, name of the drug, daily dose, and duration of treatment), details on the use of concomitant non-antihypertensive drug (presence or absence, name of the drug, and purpose of use)

2) Time points of survey

Period from the start of treatment with Zacras Combination Tablets to 12 months of treatment (or discontinuation of treatment)

* Period from 2 months before the start of treatment with Zacras Combination Tablets to 12 months of treatment (or discontinuation of treatment) for details on the use of other antihypertensive

9.2.4 Tests/Observations

9.2.4.1 Vital Signs

1) Tests/observations

Office blood pressure (systolic/diastolic), pulse rate

2) Time points of survey

Time points of measurement at the start of treatment with Zacras Combination Tablets and after 1, 2, 3, 4, 5, 6, 7, 8, 9, 10, 11, and 12 months of treatment (or discontinuation of

treatment)

9.2.4.2 Laboratory Tests

1) Test parameters

White blood cell count, platelet count, aspartate aminotransferase (AST), alanine aminotransferase (ALT), γ -glutamyl transpeptidase (γ -GTP), serum creatinine, blood urea nitrogen (BUN), serum potassium

2) Time points of survey

Time points of test from the start of treatment with Zacras Combination Tablets to 12 months of treatment (or discontinuation of treatment)

9.2.4.3 Other Observations

1) Observations

Presence or absence of pregnancy in the observation period (only females)

If pregnancy is detected during the observation period, treatment with Zacras Combination Tablets should be discontinued immediately, and Takeda's representative should be informed. The investigator shall provide detailed information (including information up to delivery such as premature delivery, wherever possible) using a pregnancy sheet at the request of Takeda's representative.

2) Time points of survey

Period from the start of treatment with Zacras Combination Tablets to 12 months of treatment (or discontinuation of treatment)

9.2.5 Adverse Events (AEs)

1) Survey items

Presence or absence of AE (refer to Table 1), AE term, date of onset, seriousness and reason for seriousness (refer to Table 2), presence or absence of discontinuation of treatment with Zacras Combination Tablets, date of outcome assessment, outcome, causal relationship to Zacras Combination Tablets * (refer to Table 3)

Patients with "not resolved" or "unknown" outcome or "unevaluable" causal relationship should be followed up wherever possible.

* For the causal relationship to Zacras Combination Tablets, the rationale for "not related" and the reason for "unevaluable" shall be collected.

Note) Additional points to consider for AEs

Abnormal worsening of target disease, for instance, worsening beyond the expected natural course of the disease, will be handled as an AE, but expected worsening of target disease should not be handled as an AE.

2) Time points of survey

Period from the start of treatment with Zacras Combination Tablets to 12 months of

treatment (or discontinuation of treatment)

Table 1 Definition of adverse events

An AE is defined as any untoward medical occurrence in a clinical investigation subject administered a drug; it does not necessarily have to have a causal relationship with this treatment.
An AE can therefore be any unfavorable or unintended sign (e.g., abnormal laboratory finding), symptom, or disease temporally associated with the use of a drug, whether or not it is considered related to the drug.
The following are also handled as AEs:
•Symptoms and so forth that occur in infants breast-fed by their mothers under treatment with a drug
•Symptoms and so forth that occur in children treated with a drug
•Symptoms and so forth that occur as a result of occupational exposure to a drug
•Symptoms and so forth that occur after administration of counterfeit medicines of our ethical drugs

Table 2 Criteria for assessing seriousness

An AE satisfying any of the following is assessed as serious:
1. Results in death (death)
2. Is life-threatening (risk of death)
3. Requires inpatient hospitalization or prolongation of existing hospitalization (hospitalization/prolonged hospitalization)
4. Results in persistent or significant disability/incapacity (disability)
5. Leads to a congenital anomaly/birth defect (congenital anomaly)
6. Is an important medical event according to 1 to 5 described above, including AEs in Takeda Medically Significant AE List

Takeda Medically Significant AE List

•Acute respiratory failure/acute respiratory distress syndrome (ARDS)	•Anaphylactic shock
•Torsade de pointes / ventricular fibrillation / ventricular tachycardia	•Acute renal failure
•Malignant hypertension	•Pulmonary hypertension
•Convulsive seizures (including convulsion and epilepsy)	•Pulmonary fibrosis (including interstitial pneumonia)
•Agranulocytosis	•Neuroleptic malignant syndrome / malignant hyperthermia
•Aplastic anemia	•Spontaneous abortion / stillbirth and fetal death
•Toxic epidermal necrolysis / oculomucocutaneous syndrome (Stevens-Johnson syndrome)	•Confirmed or suspected transmission of infectious agent by a medicinal product
•Hepatic necrosis	•Confirmed or suspected endotoxin shock
•Acute liver failure	

Table 3 Criteria for assessing the relationship of each adverse event to Zacras Combination**Tablets**

Assessment	Criteria for assessment
Related	An AE that follows a reasonable temporal sequence from administration of a drug (including the course after withdrawal of the drug), or for which possible involvement of the drug can be argued, although factors other than the drug, such as underlying diseases, concurrent illnesses, concomitant drugs, and concomitant treatments, may also be responsible
Not related	An AE that does not follow a reasonable temporal sequence from administration of a drug and/or that can reasonably be explained by other factors, such as underlying diseases, concurrent illnesses, concomitant drugs, and concomitant treatments
Unevaluable	Information necessary for evaluation, including temporal sequence from administration of a drug (including the course after withdrawal of the drug), underlying diseases, concurrent illnesses, concomitant drugs, and concomitant treatments, is not sufficient.

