Duration of disease	(Start date of treatment with Zacras - time of diagnosis of hypertension + 1) $\div 365.25$. For time of diagnosis of hypertension, 1 will be used as the day, and January 1 will be used if the month is unknown. The duration of disease will be handled as missing if the year, month, and day are unknown.
ADR, etc.	Abbreviation of “adverse drug reaction/infection” AE other than those assessed by the investigator to be not related to Zacras In this document, “adverse drug reaction/infection” is used in titles, and “adverse drug reaction, etc.” is used in the text and tables.
SAE	Adverse event assessed by the investigator to be serious Events included in the MedDRA code list in Takeda Medically Significant AE List will be handled as serious even if assessed by the investigator to be non-serious.
Number of patients with an AE or an ADR, etc.	Number of patients who experienced an AE or an ADR, etc.
Number of AE or ADR, etc.	Number of reported AE or ADR, etc.
Time of onset	Time of onset will be calculated as date of onset of AE (or ADR, etc.) - start date of treatment + 1. If the month and day of AE (or ADR, etc.) are unknown, January 1 will be used for calculation. If an AE (or ADR, etc.) occurs in the same year as treatment is started, the month and day of starting treatment will be used for calculation. If the day of AE (or ADR, etc.) is unknown, 1 will be used for calculation. If an AE (or ADR, etc.) occurs in the same year and month as treatment is started, the start date of treatment will be used for calculation. If the year, month, and day of AE (or ADR, etc.) is unknown, the start date of treatment will be used for calculation.
Patient with concurrent diabetes	Patient with a check for diabetes in the column of concurrent illness in the CRF or concurrent illness corresponding to Standardised MedDRA query (hereinafter referred to as SMQ) code 20000041 (hyperglycaemia/new onset diabetes mellitus SMQ [scope: narrow]) described
Patient with concurrent dyslipidemia	Patient with a check for dyslipidemia in the column of concurrent illness in the CRF or concurrent illness corresponding to SMQ code 20000026 (dyslipidaemia SMQ [scope: narrow]) described
Patient with concurrent hyperuricemia	Patient with a check for hyperuricemia in the column of concurrent illness in the CRF or concurrent illness corresponding to MedDRA PT code 10020903 (hyperuricaemia) described

Term	Definition

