5.3.2 Occurrence of Adverse Drug Reactions/Infections by Seriousness, Time of Onset, and Outcome

(1) Patients included in tabulation/analysis

Patients included in safety evaluation

(2) Data tabulated/analyzed

ADRs, etc. will be categorized for each variable as described below, and the type of ADR will be tabulated.

Variable	Category
Seriousness	Serious, non-serious
Time of onset	Days 1 to 180, Days 181 to 360, Day 361 or later
Outcome	Recovered, recovering, not recovered, recovered with sequelae, fatal, unknown

The type of ADR, etc. will be tabulated as described below.

Variable	Data tabulated/analyzed
Number of patients	Number of patients who experienced an ADR, etc. by SOC/PT
Number of ADR, etc.	Number of reported ADR, etc. by SOC/PT
Type of ADR, etc.	ADRs, etc. will be classified by SOC and then tabulated by PT. For laboratory tests, ADRs, etc. will be classified by SOC, then sorted by HLGT, and finally tabulated by PT. ADRs, etc. will be listed for SOC by SOC internationally agreed order and for PT in ascending order of PT code. Multiple episodes of the same ADR, etc. (PT) in the same patient will be tabulated by category as the total number of episodes (for instance, one episode of serious diarrhoea and one episode of non-serious diarrhoea in the same patient will be counted once in the respective categories).

(3) Table/figure number

Table 5.3-2

5.4 Incidence of Adverse Drug Reaction/Infection by Factors Related to Patient Demographics and Baseline Characteristics and Treatment Given

(1) Patients included in tabulation/analysis

Patients included in safety evaluation

(2) Data tabulated/analyzed

ADRs, etc. will be categorized for each variable as described below, and the incidence of ADR, etc. will be tabulated.

ADRs, etc. will be categorized for each variable as described below, and the type of ADR, etc. will be tabulated. The type of ADR, etc. will be tabulated as described in Section 5.1. For disposition of treatment with antihypertensive other than Zacras (at the start of treatment with Zacras) and disposition of treatment with antihypertensive other than Zacras (during the survey period), “other” will not be tabulated.

Variable	Category
Sex	Male, female
Age	<65 years, ≥65 years ----- <65 years, 65 to <75 years, ≥75 years
Predisposition to hypersensitivity	No, yes, unknown
Concurrent illness	No, yes

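### Table 3's Related and Not related grades can both apply to the same adverse event, with no tie-break, and the SAP's safety comparisons by renal impairment, hepatic impairment and age rest on that grade alone

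*Protocol*

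**What the plan says.** Protocol 9.2.5, Table 3, has three grades, worded identically in every protocol version in the file.

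- *Related* is satisfied by timing or, alternatively, by drug involvement that can be argued. It stays satisfied "although factors other than the drug, such as underlying diseases, concurrent illnesses, concomitant drugs, and concomitant treatments, may also be responsible".
- *Not related* is "An AE that does not follow a reasonable temporal sequence from administration of a drug and/or that can reasonably be explained by other factors", followed by the same four kinds of factor.
- *Unevaluable* is reserved for insufficient information.

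No rule says which grade prevails when two apply. Section 9.2.5 does require the rationale for each *Not related* grade, and the reason for each *Unevaluable* grade, to be collected.

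SAP 1.1 defines an ADR as "AE other than those assessed by the investigator to be not related to Zacras". *Unevaluable* events therefore count as ADRs, and *Not related* is the only grade that takes an event out.

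Protocol 10.4.2 plans the incidence of AEs, whatever their cause, by background factors that include age, renal impairment and hepatic impairment. The current SAP (the edition printed first in the file) covers this in section 5.4 for ADRs only: "ADRs, etc. will be categorized for each variable as described below, and the incidence of ADR, etc. will be tabulated". All-cause AE and SAE tables (SAP 5.1.1, 5.3.1, 5.5.1) are for the whole safety set.

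**The concern.** Protocol 3.2 sizes the survey around patients with renal impairment, patients with hepatic impairment and patients aged 75 or older, because these were the gaps left by the clinical studies. What the survey says about events in these groups comes from SAP 5.4, so it passes through the causality grade.

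The ambiguity is not spread evenly. SAP 1.1 identifies renal and hepatic impairment from the concurrent illness entries on the CRF, and Table 3 names concurrent illness among the factors that can support *Not related*. Every patient in those two groups has such a condition by definition; a patient in the comparison group need not. For age 75 or older the same is plausible but not definitional. About 250 institutions (Protocol 6.0) apply the table separately, so like events may be graded differently.

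**Working it through.** **1. Do the rows overlap?** Let T = timing is reasonable, A = drug involvement can be argued, X = reasonably explained by other factors. As written:

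- *Related* = T or A
- *Not related* = (not T) or X

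| T | A | X | Related | Not related |
|---|---|---|---|---|
| yes | yes | yes | yes | **yes** |
| yes | yes | no | yes | no |
| yes | no | yes | yes | **yes** |
| yes | no | no | yes | no |
| no | yes | yes | yes | **yes** |
| no | yes | no | yes | **yes** |
| no | no | yes | no | yes |
| no | no | no | no | yes |

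Four of the eight combinations meet both rows. Two have reasonable timing and a reasonable other explanation; two have unreasonable timing but arguable involvement. These are counts of combinations, not of events. *Unevaluable* resolves none of them, since the information is sufficient in each.

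**2. How far could ADR incidence move?** The documents state no AE or ADR rate, so there is no figure to reproduce, and the inputs here are assumptions. Let r = share of patients with an AE, c = share of those clearly related, o = share in the overlap.

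- All overlap events graded *Not related*: incidence = r × c
- All graded *Related*: incidence = r × (c + o)

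With r = 20%, c = 20%, o = 30%: 0.20 × 0.20 = 4.0%, and 0.20 × 0.50 = 10.0%. Applied to the group sizes expected in Protocol 3.2:

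| Group | Expected n | At 4.0% | At 10.0% |
|---|---|---|---|
| Renal impairment | 70 | 2.8 | 7 |
| Hepatic impairment | 100 | 4 | 10 |
| Age 75 or older | 200 | 8 | 20 |

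With r from 10% to 30%, o from 10% to 50% and c held at 20%, the range runs from 2.0–3.0% (r = 10%, o = 10%) to 6.0–21.0% (r = 30%, o = 50%).

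**3. Is the direction between groups known?** Assume that, among events with plausible timing, the overlap share is 60% in renal impairment and 20% in other patients.

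- *Equal totals of 10% in both groups.* All overlap events graded *Not related*: 10 × (1 − 0.6) = 4% against 10 × (1 − 0.2) = 8%. All graded *Related*: 10% against 10%.
- *Equal unexplained events of 8% in both groups.* Totals become 8 ÷ 0.4 = 20% and 8 ÷ 0.8 = 10%. All overlap events graded *Not related*: 8% against 8%. All graded *Related*: 20% against 10%.

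The first assumption makes the renal group look safer or equal; the second makes it look equal or worse. Nothing in the documents chooses between them.

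**The case against.** The strongest defence is that the two rows differ in degree: other factors that may also contribute leave an event *Related*, while only a reasonable explanation by other factors supports *Not related*. This is a fair reading, and it means that a merely possible other cause does not put an event in both rows. But Table 3 does not state it as a rule, and an event with plausible timing and a reasonable other explanation still meets both.

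A reader might infer that ADR incidence is therefore arbitrary. The documents do not support that. Grading is an investigator's judgement, the rationale for *Not related* is recorded, *Unevaluable* events count as ADRs, and the overall AE and SAE tables do not use causality. What stands is ambiguity that may vary between investigators.

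A reader might also infer that ADR incidence is biased low in renal, hepatic and elderly patients. Step 3 shows that this needs an assumption about the underlying event rates, which the documents do not give. The same wording equally permits these events to be graded *Related*.

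Finally, the recorded rationale might be thought a sufficient safeguard. It would help if used, but no SAP table uses it.

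**Conclusion.** The point holds as a defect of definition with a specific consequence. The two grades overlap, nothing breaks the tie, one of them alone decides whether an event is an ADR, and the current SAP gives event incidence by patient factor for ADRs only. The renal and hepatic comparisons are the most exposed, because a concurrent illness defines those groups.

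The overlap follows from the text and needs no assumption. Its size does: 4.0% to 10.0% is an illustration on assumed rates, and the direction of any effect between groups cannot be known from the documents. The absence of an all-cause table by factor, which Protocol 10.4.2 plans, is what leaves the ambiguity unchecked.

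**What to change.** In the SAP:

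1. In 5.1.2 and 5.4, add a sensitivity count of patients with an ADR that also includes *Not related* events whose collected rationale is only another possible cause and not timing. This shows how far incidence would rise, overall and by factor. It cannot show how far it might fall, since no rationale is collected for *Related*.
2. In 5.4, tabulate all-cause AE incidence by the same factors, as Protocol 10.4.2 plans. This table does not depend on the grade. The earliest SAP edition in the file (its 5.4.1) already specified one.

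The protocol's planned survey end is 31 January 2017, and the second SAP edition is dated 16 October 2017, so rewording Table 3 may come too late for these data. If it can still be changed, both rows should be made exclusive together: for example, *Related* only if drug involvement can reasonably be argued, and *Not related* otherwise, with *Unevaluable* kept for insufficient information. In step 1 that leaves no double-qualifying combination. Simply letting *Related* prevail would also break the tie, but with daily treatment over 12 months timing alone would then make most on-treatment events *Related*, and ADR incidence would approach AE incidence.

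Cost: one further table by factor and one further count. The CRF is on paper and the documents do not say that the rationale is coded, so some classification of text by judgement may be needed, under a rule fixed beforehand. The report would also carry a higher upper figure for ADR incidence.
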